IRB #: STU00204759

BIOMEDICAL PROTOCOL

PROTOCOL TITLE: Tolerance of Chlorhexidine Gluconate Versus Povidone Iodine Vaginal Cleansing Solution: a Randomized Control Trial

PRINCIPAL INVESTIGATOR:

[name]
Department of Obstetrics & Gynecology
[contact]
[contact]

VERSION NUMBER: 2

VERSION DATE: 5/09/18

STUDY SUMMARY:

Title	Tolerance of Chlorhexidine Gluconate 4% Versus Povidone Iodine 7.5% Vaginal Cleansing Solution: a Randomized Control Trial
Short Title	Tolerance of Chlorhexidine Gluconate Vaginal Cleansing Solution
Protocol Number	STU00204759
Methodology	Single-blinded Randomized Control Trial (patients blinded)
Study Duration	18 months
Study Center(s)	Prentice Women's Hospital
Objectives	Compare the tolerance of 4% chlorhexidine gluconate /4% isopropyl alcohol versus 7.5% povidone iodine vaginal cleansing solutions in patients undergoing hysteroscopy, gynecologic dilation and curettage, endometrial ablation or Essure.
Number of Subjects	Control (Povidone Iodine): 66 Experimental (Chlorhexidine Gluconate): 68
Diagnosis and Main Inclusion Criteria	Vaginal and urinary symptoms in women over the age of 18 undergoing hysteroscopy, dilation & curettage, endometrial ablation, and Essure

Study Product(s), Route, Regimen	4% chlorhexidine gluconate/4% isopropyl alcohol preoperatively
-------------------------------------	-------------------------------------------------------------------

OBJECTIVES:

Objective: To compare the tolerance of 4% chlorhexidine gluconate/4% isopropyl alcohol versus povidone iodine vaginal cleansing solutions specifically for surgical preparations in patients undergoing hysteroscopy, dilation and curettage, endometrial ablation or Essure.

- *Specific Aim 1:* To compare the frequency of patient-reported vaginal symptoms (dryness, burning, itchiness, unusual vaginal discharge) after treatment with chlorhexidine gluconate or povidone iodine vaginal cleansing solutions.
- *Specific Aim 2:* To determine the severity of vaginal symptom safter treatment with chlorhexidine gluconate or povidone iodine vaginal cleansing solutions.
- *Specific Aim 3:* To determine the presence and severity of pain or burning with urination after treatment with chlorhexidine gluconate or povidone iodine vaginal cleansing solutions.

Hypothesis: There will be no statistically significant difference between patient-reported vaginal and urinary symptoms after treatment with 4% chlorhexidine gluconate or 7.5% povidone iodine vaginal cleansing solutions.

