areas as the solution can cause irritation and sensitization. A review of chlorhexidine hypersensitivity stated possible reactions include contact dermatitis, contact urticaria, and anaphylaxis.⁶ There has also been a case report of desquamating vaginal epithelium with chlorhexidine that resulted in the planned surgery being cancelled. The patient was treated with steroids, antihistamines, and topical estrogen and the vaginal mucosa was well healed within two weeks.⁷ One study conducted in South Africa looked at the tolerance and safety of different concentrations of chlorhexidine for peripartum vaginal washes. The study concluded that those receiving 4% chlorhexidine gluconate washes had more vaginal irritation than those receiving 1% or 0.25%.⁸ Nevertheless, another study showed that non-pregnant women were able to tolerate 4% chlorhexidine gluconate solution.⁹ In fact, the American Congress of Obstetricians & Gynecologists issued a committee opinion in 2013, advocating that chlorhexidine gluconate with low concentrations of alcohol are both safe and effective for off-label use as surgical preparations of the vagina.¹⁰

Currently, surgical site infections at Northwestern's Prentice Women's Hospital are higher than the national average. One way to combat this would be to use more effective preoperative antiseptic agents. Chlorhexidine gluconate is used for surgical preparation of the vagina in patients allergic to iodine, but its application can be far-reaching. The significance of the data from this proposed study will allow us to determine the tolerance of 4% chlorhexidine gluconate compared to povidone iodine, and whether chlorhexidine gluconate is not only superior in its antiseptic properties, but also similarly or possibly more tolerable than povidone iodine.

INCLUSION & EXCLUSION CRITERIA:

Inclusion criteria: Women over age 18 who have the ability to understand and willingness to sign a written informed consent and are undergoing:

1. undergoing hysteroscopy
2. gynecologic dilation & curettage
3. endometrial ablation
4. Essure without concomitant laparoscopy

Exclusion criteria: Women who are:

1. pregnant
2. have a history of atopic dermatitis, vaginal irritation, allergic reactions, or anaphylaxis to chlorhexidine gluconate or povidone iodine.

STUDY ANALYSIS PLAN:

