The study will take place at a single site, Northwestern Prentice Women's Hospital. Using a 2-sided test to detect a difference between proportions with 80% power and a 5% significance level, and assuming the prevalence of irritation in the control group (povidone iodine) is 10% and prevalence of irritation in the exposed group (chlorhexidine gluconate) is 31%, and factoring in patients lost to follow up given that the data collection is through a survey, the study will need 68 participants in each group. There are an estimated 800 hysteroscopies at Prentice Women's Hospital each year and given incomplete follow-up, we estimate it will take 6 to 8 months of patient enrollment to achieve this desired sample size.

STUDY-WIDE RECRUITMENT METHODS:

IRB #: STU00204759

The research coordinator will contact the appropriate gynecologic surgeons who will introduce the study to potential participants during the pre-operative office visit. On the day of surgery, prior to the administration of anesthetics, the patient will be asked of their willingness to participate in the study, and a study member will explain the risks and benefits. A written informed consent form will be filled out. Participants will be randomized through the use of Excel to generate randomization numbers to either experimental antiseptic, chlorhexidine gluconate, or the control, povidone iodine.

STUDY TIMELINES:

Participants will be involved in the study on the day of their surgery to 24-48 hours after surgery.

The proposed timeline of the study can be seen below:

- April- June 2017: Communicate with gynecologic surgeons operating at Prentice Women’s Hospital to gain awareness for the study. Communicate with preoperative nurses and operating room circulating nurses to make them aware of the logistics of study.
- July-February 2018: Recruit and enroll patients. Administer patient surveys.
- March- September 2018: Compile and analyze data

STUDY ENDPOINTS:

List of study variables to be collected:

Outcomes	Type	Definition
Vaginal dryness	Ordinal	Any sensation of dryness in the vagina
Vaginal burning	Ordinal	Any sensation of burning in the vagina
Vaginal itchiness	Ordinal	Any sensation of itchiness in the vagina
Unusual vaginal discharge	Ordinal	Any witness of unusual discharge coming from the vagina
Pain or burning with urination	Ordinal	Any sensation of pain or burning with urination

Exposures	Type	Definition

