The data to be collected will include: age, gender, race, gravidity, parity, surgeon, type of surgery, concomitant cystoscopy, use of Foley catheter, name of antiseptic solution, and presence and severity of vaginal and urinary symptoms based off survey responses. The patients will receive preoperative vaginal preparation either with povidone iodine or

chlorhexidine gluconate. Both antiseptic solutions are approved for surgical preparation of the vagina at Northwestern's Prentice Women's Hospital.

DATA & SPECIMEN MANAGEMENT:

Paper data will be stored in a locked cabinet at the nursing desk of the preoperative holding area and periodically transferred to a password protected Excel file on a password-protected laptop. Paper surveys will be stored for 1 years after the end date of the data collection (September 2019) and will be discarded through the hospital's confidential document shredding service. Electronic data will be de-identified and stored indefinitely on a password-protected computer.

The data will be transitioned to Excel and analyzed with a statistical software like SPSS. The participant's MRN will be collected in order to link survey data with patient demographics and the corresponding surgery/vaginal cleansing intervention. This MRN will be matched to a participant ID, and the survey will only have the patient's ID on it. The document linking MRN with participant ID will be kept separate from the surveys. The data collection spreadsheet will not contain patient MRNs.

PROVISIONS TO MONITOR DATA TO ENSURE THE SAFETY OF PARTICIPANTS:

The PI, [name], and researchers, [name], [name], [name], and one other research coordinator will have access to the data. The study team will evaluate the data collected every 2 weeks, and look at any adverse events to ensure patient safety. Safety information will be collected with case report forms. The Principal Investigator will be notified within 24 hours of learning of any serious adverse events, regardless of attribution, occurring during the study. The office of Risk Management and the IRB will be notified as soon as possible of "any unanticipated problems involving risk to subjects or others" (UPR/UPIRSO).

Contraindications:

Contraindications include patient with a history of the following after use of chlorhexidine gluconate or povidone iodine in any application:

- Atopic dermatitis
- Vaginal irritation
- Allergic reactions
- Anaphylaxis

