The incidence of these events has not been studied specific to vaginal application.

Special Warnings and Precautions for Use:

There is a FDA warning of severe allergic reactions with chlorhexidine gluconate. Chlorhexidine gluconate continues to be used preoperatively as antiseptic agent at Northwestern operating rooms.

Chlorhexidine Gluconate and Povidone Iodine

- Do not use in contact with meninges, or over skin of head or face.
- Stop use if irritation, sensitization, or allergic reaction occurs.
- Keep out of eyes, ears, and mouth. May cause serious and permanent eye injury if placed or kept in the eye during surgical procedures or may cause deafness when instilled in the middle ear through perforated eardrums.
- If solution should contact these areas, rinse out promptly and thoroughly with water

IRB #: STU00204759

- Wounds which involve more than the superficial layers of the skin should not be routinely treated
- Repeated general skin cleansing of large body areas should not be done except when the underlying condition makes it necessary to reduce the bacterial population of the skin.

Interaction with other medications:

No studies of interactions between chlorhexidine gluconate and povidone iodine and other drugs have been conducted.

Adverse Reactions:

The FDA reports the following possible side effects with the active medications

Chlorhexidine Gluconate:

- Severe allergic reactions (rash; hives; itching; difficulty breathing; tightness in the chest; swelling of the mouth, face, lips, or tongue). It is possible that some side effects of chlorhexidine gluconate have not been reported.

Povidone Iodine:

- Severe allergic reactions (rash; hives; itching; difficulty breathing; tightness in the chest; swelling of the mouth, face, lips, or tongue). It is possible that some side effects of povidone iodine topical may not have been reported.

Adverse Event Monitoring:

Adverse event data collection and reporting, which are required as part of every clinical trial, are done to ensure the safety of Subjects enrolled in the studies as well as those who will enroll in future studies using similar agents. Adverse events are reported in a routine manner at scheduled times during a trial. Additionally, certain adverse events must be reported in an expedited manner to allow for optimal monitoring of patient safety and care. The following events meet the definition of adverse event:

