There are possible side effects to both chlorhexidine and povidone iodine. These include atopic dermatitis, vaginal irritation, allergic reactions, and anaphylaxis. There is a FDA warning of severe allergic reactions with chlorhexidine gluconate. Chlorhexidine gluconate routinely to be used preoperatively as antiseptic agent at Northwestern operating rooms. A review of anesthesia drug safety literature showed in patients who had allergic reactions after general anesthesia, chlorhexidine accounted for 5% of the allergies. Additionally, patch testing for chlorhexidine revealed a positive test in 2% of the participants suspected of contact allergic dermatitis exposed to chlorhexidine after topical application. It is estimated that this percent increases to greater than 5% in patients with atopic dermatitis, and thus patients with atopic dermatitis will be excluded in this study.¹² In another study looking at 50 cases of allergic reactions to chlorhexidine, 9 were found to have anaphylaxis.¹³ In regards to povidone iodine, one study looked patients who had a rash after exposure to povidone iodine and found 10% to have a positive patch test.¹⁴ There have been multiple case reports of anaphylaxis to povidone iodine, but no particular statistic has been reported.¹⁵ The exact incidence of the adverse events of either antiseptic in the general population still remains unknown, as well the incidence of these events with vaginal application.

POTENTIAL BENEFITS TO PARTICIPANTS:

There is no direct benefit to participants.

SHARING OF RESULTS WITH PARTICIPANTS:

The results of the study are patient-reported outcomes. Patients will not be informed on the overall study results.

SETTING:

The research study will take place at Northwestern's Prentice Women's Hospital. Antiseptic procedures will occur at Prentice operating rooms prior to surgery.

RESOURCES AVAILABLE:

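### Does the loose wording on atopic dermatitis in exclusion criterion 2 leave the trial population undefined?

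*Combined protocol and SAP*

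**What the plan says.** Three sections of the protocol use the term.

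- **Inclusion & Exclusion Criteria**, exclusion criterion 2, covers women who "have a history of atopic dermatitis, vaginal irritation, allergic reactions, or anaphylaxis to chlorhexidine gluconate or povidone iodine".
- **Contraindications**, within the section on monitoring for participant safety, gives the same four items in the same order, introduced by: "Contraindications include patient with a history of the following after use of chlorhexidine gluconate or povidone iodine in any application". The list is followed by: "The incidence of these events has not been studied specific to vaginal application".
- **Risks to Participants** uses the term twice. It first names the possible side effects of both antiseptics: "These include atopic dermatitis, vaginal irritation, allergic reactions, and anaphylaxis". It then reports a 2% positive chlorhexidine patch-test rate among people suspected of contact allergy after topical exposure, and adds: "It is estimated that this percent increases to greater than 5% in patients with atopic dermatitis". From this it concludes: "thus patients with atopic dermatitis will be excluded in this study".

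Two dates bear on timing. Study Timelines plans "July-February 2018: Recruit and enroll patients", and the title page carries "VERSION DATE: 5/09/18".

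**The concern.** In criterion 2 one qualifier, naming the two antiseptics, closes a list of four conditions. Read narrowly, it applies to all four, and atopic dermatitis excludes a woman only if it was a reaction to one of the products. Read broadly, it applies only to the later items, and any history of atopic dermatitis excludes her.

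The other sections seem to pull in different directions. The Contraindications list ties all four items to earlier antiseptic use and then calls them events, which suits the narrow reading. Risks to Participants treats atopic dermatitis as a pre-existing condition that raises the rate of positive patch tests, and excludes on that ground, which suits the broad one.

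If the sections truly conflicted, two screeners could decide differently about the same woman. Some women could then be enrolled whom the protocol says it excludes because of sensitisation. At stake would be participant protection and a clear description of who was studied.

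**Working it through.** The point rests on text, and the plan states no figure for it that could be reproduced. The check is to see which women the readings separate, whether the sentences can all hold together, and whether anything in the analysis depends on the answer.

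**Step 1: which women are in dispute.** Here a past reaction means one of the listed reactions to either antiseptic.

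| Woman's history | Criterion 2, narrow | Criterion 2, broad | Contraindications list | Risks to Participants |
|---|---|---|---|---|
| Neither | not excluded | not excluded | not listed | not excluded |
| Past reaction only | excluded | excluded | listed | silent |
| Both | excluded | excluded | listed | excluded |
| Atopic dermatitis only | not excluded | excluded | not listed | excluded |

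Only the last row differs between the readings. The same grammatical doubt touches vaginal irritation and allergic reactions, but no other section excludes on those items in wider terms.

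**Step 2: can all the sentences hold together?** For the woman in the last row:

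- The Contraindications list does not name her. It is introduced as a list that includes certain histories, so it does not claim to be complete, and it does not set eligibility. Being absent from it is not permission to enrol.
- Criterion 2 can be read either way. The broad reading is at least natural English: one speaks of an allergic reaction or anaphylaxis to an agent, but hardly of atopic dermatitis to an agent.
- Risks to Participants excludes her in so many words.

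No sentence says she may enter, and one says she may not. A team that follows every sentence leaves her out and breaks none of them. This is a reading of the text as it stands; it takes no view on which eligibility rule is clinically preferable.

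**Step 3: does the analysis depend on it?** Study-Wide Recruitment Methods describes consent on the day of surgery and then randomisation. A reading applied at screening therefore acts on both arms alike. The sample-size paragraph uses 10% versus 31% irritation, 80% power, a two-sided 5% level and an unstated allowance for loss to follow-up. None of these inputs involves atopic dermatitis.

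**Step 4: can the size be bounded?** No. The documents give no prevalence of atopic dermatitis among candidates. The 2% and greater-than-5% figures are patch-test results, not rates of vaginal symptoms, and the protocol itself says vaginal incidence has not been studied.

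**Step 5: timing.** The recruitment window follows an April to June 2017 preparation period, so it runs from July 2017 to February 2018. The version date falls after February 2018 whether it is read as May or September. If recruitment kept to plan, new wording would come too late to guide any screening decision. The documents do not show whether it did.

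**The case for a change.** The strongest reply is that Risks to Participants is not where a screener looks for eligibility. Criterion 2 is the operative text, and its closest parallel is the Contraindications list, which points to the narrow reading. A reader should not have to assemble the rule from three sections, particularly when the protocol gives a safety reason for the exclusion and clearer wording would cost one line.

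Part of this stands. Criterion 2 is poorly worded, the term is used both for a background condition and for a reaction, and a screener who had only criterion 2 in hand could take it narrowly. A sentence in the trial report saying which rule was applied would help readers describe the population.

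The rest does not carry the point further. Enrolling such a woman would mean overlooking an express exclusion elsewhere in the same protocol, and nothing shows that this occurred. The case report forms mentioned in the protocol are not reproduced, so the rule used at screening may have been explicit. If some of these women did enter, the result would still be a randomised comparison, in a slightly wider population.

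**Conclusion.** The ambiguity in criterion 2 is real but small, and it is not a contradiction. The three sections can all be followed at once, and the one sentence that speaks directly to the disputed case states an exclusion. It is a gap that a screening team can fill sensibly from the protocol as it stands. Aligning the wording would be editorial, and the choice of rule belongs to the investigator.

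The size is unknown in head-count. There is no bias between arms, and the power calculation and the primary comparison are unaffected; only the description of the population could shift slightly. This rests on two assumptions: that eligibility is settled before allocation is known, as the order of consent and randomisation implies, and that those screening worked from the whole protocol rather than from criterion 2 alone. If the second fails, the consequence is a matter for reporting who was enrolled, and the planned analysis still stands.

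### The stated 80% power belongs to a single, undefined irritation outcome and cannot be shown to apply to the hypothesis, which is judged by lack of significance across all vaginal and urinary symptoms

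*Combined protocol and SAP*

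**What the plan says.** The Study Analysis Plan specifies a two-sided comparison of two proportions with 80% power and 5% significance, "assuming the prevalence of irritation in the control group (povidone iodine) is 10"% and 31% in the chlorhexidine group. After "factoring in patients lost to follow up", at a rate it does not give, it concludes that "the study will need 68 participants in each group". The Study Summary gives "Control (Povidone Iodine): 66 Experimental (Chlorhexidine Gluconate): 68".

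The hypothesis under Objectives is wider: "There will be no statistically significant difference between patient-reported vaginal and urinary symptoms" is what the investigators expect. Specific Aim 1 is "To compare the frequency of patient-reported vaginal symptoms (dryness, burning, itchiness, unusual vaginal discharge"). Aim 2 concerns the severity of vaginal symptoms, and Aim 3 the presence and severity of urinary pain or burning. The Background section says the data will show whether chlorhexidine is tolerated similarly to, or better than, povidone iodine.

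Study Endpoints lists five ordinal outcomes: dryness, burning, itchiness, unusual discharge, and pain or burning with urination. It names no primary outcome, composite or cut-point. Procedures Involved sets three surveys: before surgery, before discharge, and at 24-48 hours. The pre-operative form (Appendix 1) asks about the past 7 days. The post-operative form (Appendix 2) asks about the time from the end of surgery to the moment of answering.

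**The concern.** A sample-size statement tells the reader what one particular comparison can detect. Here the comparison has no definition. Irritation appears as background, as an exclusion, as a side effect and in product warnings, but never as an endpoint or survey item. Several different analyses could each be presented afterwards as the powered one.

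The direction of the hypothesis makes this more serious. The investigators expect no significant difference, and the Background looks to the data for evidence of similar tolerability. No margin is stated, so lack of significance is the only criterion on offer. The main risk is then that a real difference is missed and the result is reported as similar tolerance. Whether the plan guards against that depends on the power for the outcome actually analysed, and the documents do not let a reader work that out.

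**Working it through.** **Inputs from the protocol.** p1 = 0.10, p2 = 0.31, difference d = 0.21, two-sided 5% (z = 1.960), 80% power (z = 0.842), 68 per group. The loss rate and the test are not stated. All other rates below are assumptions.

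**1. Reproduce the 68.** Mean rate 0.205.

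- Pooled formula: n = [1.960·√(2·0.205·0.795) + 0.842·√(0.10·0.90 + 0.31·0.69)]² / 0.21² = (1.119 + 0.464)² / 0.0441 = 56.8, so 57 per arm.
- Continuity-corrected: (56.8/4)·[1 + √(1 + 4/(56.8·0.21))]² = 66.0, so 66 per arm.
- Fisher's exact test: 64 per arm (exact power 80.4%).

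The room left for loss within 68 is 1 − 57/68 = 16.2%, 1 − 66/68 = 2.9%, or 1 − 64/68 = 5.9%. With 15% loss, 57/0.85 = 67.1, which rounds up to 68. The figure is sound for one binary outcome at these rates. Because test and loss are unstated, the results below are given for 57 evaluable per arm, with 68 in brackets.

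**2. What a non-significant result would mean.** Power = Φ[(d√n − 1.960·√(2p̄(1−p̄))) / √(p1(1−p1) + p2(1−p2))].

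- 10% vs 31%: (1.585 − 1.119)/0.551 = 0.846, power 80%. At 68: (1.732 − 1.119)/0.551 = 1.111, power 87%.
- 10% vs 20%: (0.755 − 0.990)/0.500 = −0.469, power 32%. At 68: (0.825 − 0.990)/0.500 = −0.330, power 37%.

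**3. Precision if the two arms have equal rates.** Half-width of the 95% confidence interval = 1.96·√(2p(1−p)/n).

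| Rate in both arms | 57 per arm | 68 per arm |
|---|---|---|
| 10% | 11.0 points | 10.1 points |
| 20% | 14.7 points | 13.4 points |
| 30% | 16.8 points | 15.4 points |

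At 10%, even identical observed rates would leave a doubling inside or at the edge of the interval.

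**4. If the endpoint's control rate is not 10%.** A composite of several symptoms could be more common than any one of them. The effect on power depends on what is held fixed. The planning rates imply an odds ratio of (0.31/0.69)/(0.10/0.90) = 4.04.

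| Control rate | Gap fixed at 21 points | Odds ratio fixed at 4.04 |
|---|---|---|
| 10% | 80% (87%) | 80% (87%) |
| 20% | 20% vs 41%: 69% (76%) | 20% vs 50.3%: 93% (97%) |
| 30% | 30% vs 51%: 63% (71%) | 30% vs 63.4%: 96% (98%) |

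The documents do not say which pattern to expect, so power could move either way.

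**5. The 66 and the 68.** For 10% vs 31% without loss, 66 controls and 68 experimental give 86.1% power, against 86.7% for 68 and 68. The conflict matters little for power, but the two sections cannot both be right.

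**The case against.** **There is a link between irritation and the survey.** The Background moves from the risk of vaginal irritation to patient-reported vaginal and urinary symptoms, and the powering sentence itself says the data come from a survey. The endpoint definitions speak of any sensation, and Aim 1 of frequency, which suggests a none-versus-any split. This stands: irritation is loosely tied to survey-reported symptoms. It does not settle the item or composite, or the survey, and the cut-point is only hinted at.

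**The two post-operative surveys are nested.** Both ask for the worst severity since surgery, so the 24-48 hour survey already covers the time before discharge. This narrows the ambiguity and makes that survey a natural choice, but the plan does not make the choice or give a rule for symptoms already present before surgery.

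**The power might apply after all.** The hypothesis can be read as one overall comparison. If irritation meant any listed symptom, the 80% and 5% could belong to it. A reader might therefore infer too much from a flat statement that the power does not apply. The documents support only that it cannot be shown to apply.

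**Two further inferences go beyond the text.** One is that a commoner endpoint must have lower power; step 4 shows that this holds for a fixed gap and reverses for a fixed odds ratio. The other is that the false-positive rate is inflated by testing five symptoms at 5% each. Five independent tests would give 1 − 0.95⁵ = 22.6%, but no section states such a plan, and only Aim 1 says the symptoms will be compared.

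**Timing.** "VERSION DATE: 5/09/18" falls inside "March- September 2018: Compile and analyze data", so a reader might infer that any endpoint named now is post hoc. Data & Specimen Management, however, sets the discard of paper surveys one year after data collection ends and attaches September 2019. On either reading of that date, collection ran to September 2018 or later. The dates do not settle the matter.

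**Conclusion.** The concern holds in this form. The sample size is arithmetically sound for a single 10% vs 31% comparison, but the outcome it refers to is not defined well enough to analyse, and the stated 80% power at two-sided 5% cannot be shown to apply to the hypothesis. As written, the plan could lead to a claim of similar tolerance resting on non-significance alone. At 57 (68) evaluable per arm, that result is compatible with differences that might matter: a doubling from 10% to 20% would be missed 68% (63%) of the time.

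It would be too strong to say that the trial can show nothing about similarity. With equal observed rates between 10% and 30%, the interval would exclude a 21-point difference, since the half-widths run from about 10 to 17 points. What is missing is a statement, made in advance, of the difference that has to be excluded.

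These sizes rest on normal approximations, on assumed control rates, and on an evaluable number between 57 and 68 per arm, because the loss rate is not given.

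**What to change.** 1. Name one primary binary endpoint at one survey. One example is any Aim 1 vaginal symptom above the lowest response category on the 24-48 hour survey, whose recall window already covers the whole post-operative period. State how symptoms reported before surgery count.
2. Fix and date this endpoint before results by arm are seen. If they have been seen, label it post hoc.
3. Reword the hypothesis to this endpoint and judge it by the difference in proportions with its 95% confidence interval. Claim similar tolerance only if the interval excludes a difference stated in advance; otherwise report the result as inconclusive.
4. Report the other symptoms, including pain or burning with urination, and the other post-operative survey as secondary with 95% confidence intervals. Make no significance claims for them unless an adjusted or ordered testing rule is stated.
5. Restate power or precision for the chosen endpoint over a range of control rates, with the test, the assumed loss and the evaluable number per arm.
6. Reconcile the control-arm size of 66 in the Study Summary with the 68 in the Study Analysis Plan.

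The cost is wording and one recalculation, with no extra patients if the size is kept. The stated power may become less favourable, secondary symptoms may lose stand-alone significance claims, and the endpoint may have to carry a post hoc label.
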